### **7.3.1. Pregnancy Testing**

All pregnancy tests (serum *and* urine) used in this study must have a sensitivity of **at least 25 mIU/mL**, and must be performed using supplied offered by the sponsor-identified central laboratory certified laboratory.

***For female subjects of childbearing potential***, following a negative pregnancy test result ***and*** after confirmed eligibility based on Visit 2 (Screen 2) tests(s), appropriate contraception must be commenced and the second negative pregnancy test result will then be required prior to randomization. ***In addition, at a minimum***, 2 negative *serum* pregnancy tests (ie, negative pregnancy test at Visit 1 and Visit 4) ***plus*** a negative *urine* at Visit 4 (Day -14) and Visit 5 (Day 1; randomization) are required before receiving double-blind IP – starting on Day 1. In the absence of regular menstrual bleeding, the female subject should have used highly effective method of contraception (refer to [Section 4.4.6](#)) for **at least 28-days** before Visit 4 (Day -14).

Pregnancy tests will be performed at times defined in the [Schedule of Activities \(Table 2\)](#) to confirm that the subject has not become pregnant during the study. Pregnancy tests will also be done whenever 1 menstrual cycle is missed during the active treatment period (ie, Day 1 through Week 16, inclusive) and when potential pregnancy is otherwise suspected, and may be repeated if requested by institutional review boards (IRBs)/ethics committees (ECs) or if required by local regulations. In the case of a positive confirmed pregnancy, the subject will be withdrawn from administration of investigational product and from the study.

### **7.4. Rater Qualifications**

In this study, the AUDIT questionnaire will be completed by the site staff based on responses offered by the subjects – at the visits outlined in the [Schedule of Activities \(Table 1\)](#). Training for the site staff completing this questionnaire will be offered by the sponsor as part of the protocol-specific training ahead of the initiation of the study.

CCI

CCI

## 7.6. Exploratory Biomarkers

Blood samples for exploratory biomarkers – including NASH-related biomarkers, potential mechanism-related parameters, metabolic parameters, and exploratory markers of liver function – will be collected at the nominal time points defined in the [Schedule of Activities \(Table 2\)](#). Refer to list of endpoints outlined in [Section 2](#) that encompass these exploratory biomarkers.

- These samples must be processed and shipped as indicated in the study-specific laboratory manual provided to the investigator site, prior to initiation of study, to maintain sample integrity:

- Any deviations from the sample handling procedure (eg, sample collection and processing steps, interim storage or shipping conditions), including any actions taken, must be documented and reported to the sponsor. On a case-by-case basis, the sponsor may make a determination as to whether sample integrity has been compromised. Any deviation from the specified sample handling procedure resulting in compromised sample integrity will be considered a protocol deviation;
- Any *scheduled* collection prior to next dose of blinded investigational product, if undertaken post dose, will be captured as a protocol deviation even if results are deemed evaluable;
- Refer to [Section 6.1](#) for proposed chronology of procedures for nominal time points when these collections coincide with other procedures;
- Samples will be analyzed using a validated analytical method (which need **not** meet Good Laboratory Practice (GLP) standards, especially for these exploratory endpoints) but in all cases, the method will be in compliance with Pfizer standard operating procedures.

CCI

CCI

CCI

CCI

### **7.8. Blood Volume**

In this study, the total blood sampling volume for individual subjects will be approximately **400 mL**. This includes approximately **40 mL** blood drawn across the clinical laboratory tests at the pre-Qualification; and the remaining approximately **360 mL** blood drawn from Visit 1 (Screen 1) through the On-site Follow-up visit, inclusive.

Additional blood samples may be taken **for safety assessments, only**, provided the total volume taken during the study does **not** exceed 550 mL.

## **7.9. Specific Subject Safety Scenarios**

### **7.9.1. Potential Cases of Thrombocytopenia**

While thrombocytopenia (defined as platelet count below 100,000/mm^3) has **not** been observed in the completed Study C1171001, in the current study, platelet count as reported by the sponsor-identified central laboratory, with or without any accompanying signs/symptoms, will be assessed versus the threshold outlined in [Appendix 2](#) every two weeks post randomization (on Day 1 / Visit 5) up to Visit 9 (Week 8) and monthly thereafter (Visit 10 / Week 12 and Visit 11 / Week 16).

- In subjects **observed** to have platelet count below the LLN at Visit 9 (Week 8), unplanned visits at Week 10 and Week 14 (*in addition* to the scheduled Visit 10 [Week 12] and Visit 11 [Week 16]) should be used to –
  - Inquire about adverse events via open-ended inquiry;
  - *And* collect blood sample to permit safety-related laboratory assessments included hematology panel assessment by the sponsor-identified central laboratory.

Subjects observed to have a decline over time ultimately reaching the threshold of < 75,000/mm^3 in platelet count as outlined in [Appendix 2](#) should be withdrawn with the primary reason for withdrawal captured as an adverse event of thrombocytopenia.

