### 3.2. Stopping Rules for Dosing in Individual Subjects

At investigator discretion, ***for subjects' safety***, dosing with double-blinded investigational product (ie, post randomization), may be stopped in an individual subject – either temporarily **or** permanently. In such cases, any open TEAEs must be followed to resolution or until such time that the event is viewed to have stabilized – refer to [Section 8](#) for details – specifically, [Section 8.1](#) which outlines the requirements for reporting adverse events, [Section 8.2.3](#) detailing definition of serious adverse events, and [Section 8.4.2](#) summarizing management of potential cases of drug-induced liver injury which are categorized as potentially important medical events.

An example where **temporary discontinuation of dosing** with investigational product, may be considered appropriate includes hospitalization with subsequent discharge within  $\leq 7$ -days in stable medical condition, as determined by medically-qualified investigator. Of note, in this study, re-challenge/re-initiation of dosing with double-blinded investigational product should **not** be attempted in subjects who meet threshold for withdrawal based on platelet count ([Appendix 2](#)) *or* fasting serum triglycerides ([Appendix 3](#)).

Examples where **permanent discontinuation of dosing** and withdrawal of the subject from the study is deemed appropriate, as determined by investigators' medical judgment, include:

- Hospitalization due to serious adverse event (SAE) resulting in clinical decompensation of the subject *and* necessitating continued inpatient stay for more than 7-days;
- Subjects observed to have a decline over time ultimately reaching the threshold of  $< 75,000/\text{mm}^3$  in platelet count – refer to [Section 7.9.1](#) and [Appendix 2](#) for additional guidance;
- Individual subjects with consistently increasing fasting serum triglycerides over time ultimately reaching the threshold of  $\geq 800$  mg/dL (9 mmol/L) – refer to [Section 7.9.2](#) and [Appendix 3](#) for additional guidance;
- Of note, in both the above cases of pre-identified laboratory thresholds, 1 additional unplanned assessment may be warranted *before* permanent withdrawal if the threshold is observed to be met as an isolated occurrence relative to all prior results *and* subject is asymptomatic.

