### **7.9.2. Potential Cases of Hypertriglyceridemia**

In Study C1171001, gradual increases in fasting and post-prandial serum triglycerides have been observed – refer to [Section 1.2.2](#). Hence, in the current study, fasting serum triglycerides as reported by the sponsor-identified central laboratory, with or without any accompanying signs/symptoms, will be assessed versus the threshold outlined in [Appendix 3](#).

Individual subjects with consistently increasing fasting serum triglycerides over time ultimately reaching the threshold of ≥ 800 mg/dL (9 mmol/L) as outlined in [Appendix 3](#) should be withdrawn with have the primary reason for withdrawal captured as an adverse event of hypertriglyceridemia.

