5.2.2 Analyses for Categorical Data

Categorical data will be summarized by presenting the number of subjects and the percentage.

The Wilcoxon rank sum statistic will be used to assess the randomized arm difference in the distribution (median) of the number of hypoglycemic events per subject.

The Wilcoxon rank sum statistic will be used to assess the randomized arm difference in the distribution (median) of the number of thrombocytopenia events per subject.

The Wilcoxon rank sum statistic will be used to assess the randomized arm difference in the distribution (median) of the number of hypertriglyceridemia events per subject.

Hypoglycemic risk ratio, thrombocytopenia risk ratio, and hypertriglyceridemia risk ratio may be estimated by analysis methods based on a counting process approach (Andersen and Gill, 1982) for analyzing recurrent events (using the robust sandwich estimate of the covariance matrix by Lin and Wei (1989) in order to take into account the non-independence of multiple events for a single subject).

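### SAP 5.2.2 compares arms on thrombocytopenia and hypertriglyceridemia events per subject, but withdrawal at the platelet or triglyceride limit cuts those counts short, so they need not rise with severity

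*Protocol*

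**What the plan says.** Protocol 7.9.1 defines thrombocytopenia as a platelet count below 100,000/mm³. It says that a subject who declines to below 75,000/mm³ "should be withdrawn with the primary reason for withdrawal captured as an adverse event of thrombocytopenia". Section 7.9.2 treats triglycerides in the same way: a subject whose fasting values keep rising, "ultimately reaching the threshold of ≥ 800 mg/dL (9 mmol/L"), is to be "withdrawn with have the primary reason for withdrawal captured as an adverse event of hypertriglyceridemia". Section 3.2 lists both as cases of permanent discontinuation and withdrawal from the study. It adds that restarting blinded drug should not be "attempted in subjects who meet threshold for withdrawal based on platelet count" or on triglycerides.

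SAP 5.2.2 uses the Wilcoxon rank sum statistic to assess the "difference in the distribution (median) of the number of thrombocytopenia events per subject", and does the same for hypertriglyceridemia. It continues: "Hypoglycemic risk ratio, thrombocytopenia risk ratio, and hypertriglyceridemia risk ratio may be estimated by analysis methods based on a counting process approach", with a robust variance. The readable text does not say what one event is. It gives no exposure term for the Wilcoxon test and no rule for a subject whose count ended because the limit was reached.

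**The concern.** Falling platelets and rising triglycerides are the two adverse drug reactions that Protocol 1.4 identifies, and this is a dose-ranging study. A between-arm test for them should move towards harm as the harm becomes more severe.

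A count per subject may not do so, because the worst results stop the counting. The Wilcoxon test ignores how long each subject was observed. The Andersen-Gill model does use time at risk, but it treats the end of follow-up as unrelated to the event process, and here the event itself ends follow-up. Section 7.9.1 also adds Week 10 and Week 14 tests for subjects below the lower limit of normal at Week 8. If unplanned samples count, subjects with milder, lasting abnormalities gain chances to score after severe cases have left.

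**Working it through.** The documents state no event rate or power for these comparisons, so there is no planned figure to reproduce.

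**Inputs from the documents**
- 72 subjects per arm (Protocol 9.1).
- Post-baseline laboratory visits at Days 14, 28, 42, 56, 84 and 108 (Protocol Table 2).
- SAP Table 2 levels: platelets <100 and <75 ×10³/mm³; triglycerides ≥400, ≥600 and ≥800 mg/dL.
- Triglycerides up to 400 mg/dL allowed at entry and at randomization (Protocol 4.1 and 4.3).

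**Assumptions:** an event is one visit beyond the Flag level, and the affected proportions are those given below.

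**1. Wilcoxon test.** The effect is θ = P(dose > comparator) + ½P(tie); above 0.5 means that the dose looks worse. Let a fraction *q* of the dose arm score fewer events than each of the affected fraction *p* of the comparator, with everyone else at zero. Then

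θ = 0.5 + 0.5 × [q(1 − p) − p],

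which is below 0.5 only if q < p/(1 − p).

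- Event-free placebo (p = 0), q = 10/72: θ = 0.5 + 0.5 × 0.139 = 0.569, two-sided P = 0.0011. The result is the same whether each affected subject scores 1 or 4.
- p = 10/72 with 4 events each, q = 10/72 withdrawn after 1: θ = 0.5 + 0.5 × (0.1196 − 0.1389) = 0.490. Mean counts are 10/72 = 0.14 and 40/72 = 0.56. Had the severe cases scored 5 instead, θ would be 0.510. P = 0.74 either way.
- The reversal limit for p = 10/72 is 72 × 10/62 = 11.6, so up to 11 of 72 (θ = 0.496 at 11). For p = 14/72 it is 72 × 14/58 = 17.4, so up to 17 of 72.
- q = 18/72 against p = 11/72 with 5 events each: θ = 0.5 + 0.5 × (0.2118 − 0.1528) = 0.53. The more toxic dose still ranks worse.

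**2. Optional rate, platelets.** Suppose a fraction *a* of each arm is affected. In one arm they stay mildly low from Week 4 (5 visits). In the other they are withdrawn at Day 28 after 1 event. The ratio of the mild arm's rate to the severe arm's is

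5 × [(1 − a) × 108 + a × 28]/108.

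This is 4.8 at a = 5%, 4.6 at 10% and 3.9 at 30%. If a repeat or early-termination sample also counts, the 10% figure falls to 4.63/2 = 2.3 with 2 events per withdrawn subject, or 4.63/3 = 1.5 with 3.

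**3. Optional rate, triglycerides.** Suppose 15% of each arm sit near 400 mg/dL and are flagged at half of visits. On active, two-thirds of them (10% of the arm) reach 800 mg/dL at Week 4 and leave.

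- Placebo: 0.15 × 6 × 0.5 = 0.45 events per subject.
- Active: 0.05 × 3 + 0.10 × (0.5 + 1) = 0.30 events, over 0.90 + 0.10 × 28/108 = 0.926 of full follow-up.
- Rate ratio: (0.30/0.926)/0.45 = 0.72, although 10% against 0% reached the limit.
- One extra counted sample per withdrawn subject gives (0.40/0.926)/0.45 = 0.96; two give 1.20.

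In simulated trials of this case the active rate was below placebo in about 77% (53% with one extra sample, 33% with two). The Wilcoxon test, at a one-sided 10% level borrowed from the primary endpoint, pointed to harm in about 7%. A subject-level comparison at the withdrawal limit did so in about 93%.

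**4. Truncation of the mean.** In simulated platelet courses stopped at the first value below 75,000/mm³, mean events per subject were 0.26, 0.52 and 0.93 as the drug effect grew. Without stopping they were 0.38, 0.84 and 1.45. Against placebo without events, θ was the same with and without stopping.

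**The case against.** A reader might infer that the worst-affected subjects score the fewest events of all. They do not. A count below 75,000/mm³ is already thrombocytopenia, so a withdrawn subject scores at least 1 and an unaffected subject scores 0. In the simulated courses, withdrawn subjects averaged 2.1 to 2.2 events, against 1.6 to 1.9 for affected subjects who stayed. Counting may also run a little past the limit: Protocol 3.2 allows one repeat assessment, Table 2 has an early-termination sample, and AEs are collected for at least 28 days after the last dose.

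A reader might also infer that these counts are the only between-arm evidence on the two harms, so that a toxic dose could pass unseen. The SAP does not support that:
- 6.3.2.1 fits an MMRM to fasting triglycerides, with ratios to placebo.
- 6.6.1 gives risk differences for Tier-1 and Tier-2 TEAEs. Tier 2 needs only 4 subjects in any arm, and threshold withdrawals are recorded as AEs. At 7/72 against 0/72, Fisher's exact P is 0.013.
- 3.4.2 counts subjects at each Flag and Alert level, and 6.5.1 reports withdrawal reasons.
- The review committee receives the platelet and triglyceride withdrawals (7.2).

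The definition of an event matters as much. Protocol 8.2.2 says that merely repeating an abnormal test is not in itself an AE. If an event is an AE episode, most affected subjects score 1 and little is lost. The platelet scenario is also extreme, since Protocol 1.2.2 reports no platelet decrease up to 40 mg/day and the top dose here is 50 mg. SAP 6.6.2.1 on platelets is redacted and may add analyses.

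All of this stands and limits the consequence. It does not supply a definition of an event or a rule for withdrawn subjects in 5.2.2. Nor does it make the tests named there rise reliably with severity.

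**Conclusion.** The point holds as a weakness of the stated comparison. It is not a route by which harm would go unnoticed. If out-of-range visits are counted, withdrawal at the limit lowers the counts of severe cases relative to milder persistent ones. For the Wilcoxon test the main effect is lost sensitivity; it reverses only in near-ties such as 11 against 10 of 72. The larger reversals belong to the Andersen-Gill ratio, which is optional.

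The exposure lies mainly in dose-to-dose comparisons and in triglycerides. Entry is allowed up to 400 mg/dL, which is also the Flag level, so repeated flags on placebo are likely. Protocol 1.2.2 reports triglyceride rises at 40 mg/day and above, a range that includes the 50 mg arm.

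The figures rest on visit-level counting, on assumed proportions affected, and on withdrawal at Week 4 after one or two events. Counting repeat or early-termination samples weakens them, and two extra samples per subject bring the triglyceride ratio back above 1. The change is worth making because it is cheap and these are the drug's identified reactions.

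**What to change.** In SAP 5.2.2:
1. Define an event for each harm (out-of-range visit or AE episode), and say whether unplanned, repeat and early-termination samples count.
2. Make the between-arm comparison the proportion of subjects crossing each SAP Table 2 Flag and Alert threshold, as a risk difference with confidence interval. A subject withdrawn at the limit has already crossed every lower threshold for that parameter, so withdrawal at the limit does not shrink this measure.
3. Add a rank test on each subject's worst post-baseline value (platelet nadir, triglyceride peak), with threshold withdrawals ranked worst.
4. Optionally add time to first crossing, which also deals with follow-up shortened for other reasons.
5. Keep event counts and rate ratios for these two harms as description only.

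Check the result against the redacted 6.6.2.1 for overlap. The cost is SAP wording and a few extra outputs from data already collected. Visits, sampling and withdrawal rules stay as they are.

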### **7.9.2. Potential Cases of Hypertriglyceridemia**

In Study C1171001, gradual increases in fasting and post-prandial serum triglycerides have been observed – refer to [Section 1.2.2](#). Hence, in the current study, fasting serum triglycerides as reported by the sponsor-identified central laboratory, with or without any accompanying signs/symptoms, will be assessed versus the threshold outlined in [Appendix 3](#).

Individual subjects with consistently increasing fasting serum triglycerides over time ultimately reaching the threshold of ≥ 800 mg/dL (9 mmol/L) as outlined in [Appendix 3](#) should be withdrawn with have the primary reason for withdrawal captured as an adverse event of hypertriglyceridemia.

### **7.9.3. Management of Glycemic Control in Patients with T2DM**

Events of hypoglycemia (HAE) and fasting plasma glucose will be routinely monitored during participation in the study, in subjects with T2DM. At Visit 3 / Run-in, subjects will be given the following instructions/guidance to be complied with for the duration of participation in the study:

- Subjects will be provided the following (as provided to the sites by the sponsor).
- To aide in management of their T2DM the following (or similar) items:

- Home glucose monitoring supplies including a sponsor-provided, plasma-referenced, home glucometer and accompanying supplies;
  - Diary to be completed at home for any symptomatic episodes and brought to **each** visit to the site along with the glucometers;
  - Instructions on use and documentation of home glucose monitoring results;
  - Low blood glucose information sheet which delineates the symptoms of hypoglycemia along with treatment options **and** instructions to share with their family member(s) / roommate(s) to help in their management of hypoglycemia;
  - Recommended frequency for routine home glucose monitoring will be determined for each subject by the investigator, however, a frequency of **at least once per day** should be *emphasized*;
  - Home glucose monitoring must be undertaken in the event subjects' experience symptoms of HAE, whenever possible; these symptoms must be captured in the diary.
- Routine safety monitoring (eg, liver function monitoring) for any background medications, including anti-diabetic agents, is the responsibility of the investigator and should be consistent with guidelines found in prescribing information for the respective agents;
  - ***Wherever possible***, new agents for glycemic control *or* change in doses of concomitant agents for glycemic control (refer to [Section 5.8.1](#)) should be avoided during participation in the study unless protocol-specific criteria for inadequate glycemic control are met – refer to [Section 7.9.3.1](#).

#### **7.9.3.1. Protocol-Specific Criteria for Inadequate Glycemic Control**

Investigators must review the diary completed by the subjects and the readings stored in the glucometer devices at **each** visit after the Run-in Visit. Based on this information, as well as review of the results reported by the central laboratory, an assessment of any symptomatic and asymptomatic occurrence of hypo- or hyper- glycemia must be undertaken.

##### **7.9.3.1.1. Management of Hypoglycemia (HAE)**

Any episode of HAE must be captured with sufficient detail as outlined in [Appendix 4](#). For definition of HAE and severity categorization, refer to [Section 7.9.3.1.2](#), below.

##### **7.9.3.1.2. Definition and Severity Categorization of HAE**

Based on review of the subject completed diary at **each** visit to the site as well as results reported by the central laboratory, the investigator must assess the glucose values as well as any symptoms documented.

HAE is defined as **one** of the following:

1. **Asymptomatic hypoglycemia:** An event *not* accompanied by typical symptoms of HAE but a plasma glucose reading of  $\leq 49$  mg/dL (2.7 mmol/L) using sponsor-provided, plasma-referenced, home glucometers (or sponsor-identified central laboratory);
2. **Documented symptomatic hypoglycemia:** An event during which typical symptoms of HAE are accompanied *with* a glucose reading of  $< 70$  mg/dL (3.9 mmol/L) using sponsor-provided, plasma-referenced, home glucometers (or sponsor-identified central laboratory) **and** the clinical picture includes prompt resolution with food intake, subcutaneous glucagon, or intravenous glucose;
3. **Probable symptomatic hypoglycemia:** An event during which symptoms of HAE are *not* accompanied by a plasma glucose determination, but was presumably caused by a plasma glucose concentration of  $< 70$  mg/dL (3.9 mmol/L) using sponsor-provided, plasma-referenced, home glucometers (or sponsor-identified central laboratory) **and** the clinical picture includes prompt resolution with food intake, subcutaneous glucagon, or intravenous glucose.

**NOTE: Pseudo-hypoglycemia:** An event during which symptoms consistent with HAE are reported along *with* a plasma glucose reading  $\geq 70$  mg/dL (3.9 mmol/L) using sponsor-provided, plasma-referenced, home glucometers (or sponsor-identified central laboratory) *may* be reported as an adverse event (AE) of HAE but will **not** be considered as having met the protocol definition of HAE offered above.

*Each episode* of HAE must be characterized with respect to severity. In order to characterize the event as 'severe', **all three (3)** criteria below must be met:

1. The subject was unable to treat him/herself. Neurologic impairment, and not the age of the subject, is the explanation for why the subject could not treat him/herself and required the assistance of another person.
2. The subject exhibited at least **one** of the following neurological symptoms:
  - Memory Loss;
  - Confusion;
  - Uncontrolled behavior;
  - Irrational behavior;
  - Unusual difficulty in awakening;
  - Suspected seizure;

- Seizure;
  - Loss of consciousness.
3. Either:
- **If** blood glucose was measured and was  $\leq 49$  mg/dL (2.7 mmol/L) using sponsor-provided, plasma-referenced, home glucometers (or central laboratory) **or**
  - **If** blood glucose was **not** measured, the clinical manifestations were reversed by oral carbohydrates, subcutaneous glucagon, or intravenous glucose.

Events that do **not** meet **all** the criteria above for ‘severe’ HAE are characterized as ‘mild’ or ‘moderate’ in severity.

